### **11.4.4 Physical examination**

The physical examination baseline is defined as the last examination result before the first administration.

The physical examination will be summarized by the normal/abnormal changes before and after treatment.

The abnormal results of physical examination will be listed.

### **11.4.5 12-Lead ECG**

Baseline is defined as the most recent test data before the first dose.

Items concerning ECG include: HR (times/min), PR interval (ms), QT interval (ms), and QTc (ms). The measured value and change from baseline of each ECG variable at each time point will be summarized using descriptive statistics. At the same time, ECG will be summarized by the normal/abnormal changes before and after treatment.

If QTcF is not directly provided on the ECG report, it will be obtained using the following formula (Fridericia formula):

$$QTcF = QT/(RR^{1/3})$$

RR = 60/heart rate (s)

Related data will also be reported in the form of listing.

### **11.4.6 ECOG PS**

Baseline is defined as the most recent test data before the first dose.

The ECOG PS of each cohort will be analyzed by descriptive statistics.

All ECOG PS will be reported in the form of listing.

### **11.4.7 Other safety data**

Examinations such as echocardiography, virology, fecal occult blood, pregnancy, and coagulation function will be listed.

## 11.5 Efficacy Analysis

The tumor assessment at each time point will be conducted by the investigator as per RECIST (v1.1). The descriptive statistics of ORR will be summarized by stages (Stage I: 19 subjects respectively in cohort 1 and cohort 2 who have completed the response evaluation; Stage II: the remaining subjects who have completed the response evaluation) and cohorts, while PFS, DoR, and DCR will be only summarized by cohort. The efficacy analysis will be carried out based on FAS. If a subject's baseline or post-baseline tumor assessment is missing, the subject's is non-evaluable (NE) in response. For the maximum post-baseline change in the sum of the longest diameter of the target lesion, a waterfall plot will be drawn by cohort; for the post-baseline change in each visit regarding the sum of longest diameter of the target lesion relative to the baseline, a spider chart will be drawn by cohort.

### 11.5.1 Primary efficacy endpoint analysis

#### 11.5.1.1 Best overall response (BOR)

BOR is defined as the best response recorded from the start of the treatment until objective recording of progressive disease (PD) by RECIST (v1.1) or start of subsequent anti-cancer therapy (whichever occurs first). For subjects without documented progression or new anti-cancer treatment, BOR will be determined based on all response evaluations. BOR recorded during this period will be based on the confirmed response. For the criteria for response confirmation, see Appendix 1.3.

- Confirmed CR: Response evaluated as CR and reconfirmed as CR at a later time point (at least 4 weeks later and before PD).
- Confirmed PR:
  - Response evaluated as CR but reconfirmed as PR (CR not reached) at a later time point (at least 4 weeks later and before PD).
  - Response evaluated as PR but reconfirmed as CR/PR at a later time point (at least 4 weeks later and before PD).
- Confirmed SD:
  - Response evaluated as CR/PR but reconfirmed as SD (CR/PR not reached).
  - Response evaluated as SD at least once within 5 weeks after the start of the study (visit window: 6 weeks - 7 days).
- PD: Progressive disease not meeting the requirements for confirmed CR, PR, and SD
- NE: Other conditions

A response will be judged as PR, if a patient has two non-consecutive results of PR, the interval between the two is more than four weeks, and no PD occurs during the interval. Similarly, a response will be judged as CR, if a patient has two non-consecutive results of CR, the interval between the two is more than four weeks, and no PD occurs during the interval.

CR or PR occurring after the start of subsequent anti-cancer treatment will not be included in the calculation of BOR.

BOR (CR, PR, SD, PD, and NE) will be analyzed by frequency and percentage.

#### **11.5.1.2 Objective response rate (ORR)**

ORR is defined as the proportion of subjects whose BORs have been confirmed as CR or PR by RECIST (v1.1).

When the first response evaluation data of a subject after treatment are missing or unknown, the subject is not evaluable (NE) and will only be included in the denominator for percentage calculation.

ORR of a single cohort and its two-sided 95% exact (Clopper-Pearson) confidence interval will be calculated.

The confirmed CR, PR, SD, and PD will be listed and summarized.

The analysis for ORR will be repeated based on FAS, PPS, and ES.

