7 STUDY EVALUATION

7.1 Efficacy Evaluation

7.1.1 Efficacy endpoints

The primary efficacy endpoint of this study is objective response rate (ORR).

Objective response rate (ORR): the proportion of treated subjects with a best overall response (BOR) of complete response (CR) or partial response (PR) as per RECIST 1.1 criteria. If the subject achieves CR or PR, conformation should be done at least 4 weeks (28 days) after the first evaluation. Best overall response refers to the best response assessed by the investigator, or the best response from the date of enrollment to the first documentation of progression as per RECIST 1.1 or to the start of a new anti-tumor treatment (whichever comes first). For subjects without documented progression or new anti-cancer treatment, BOR will be determined based on all response evaluations. For subjects who continue SHR-1210 treatment beyond progression, the best overall response should be based on the efficacy assessment at the time of first documented progression as per RECIST 1.1. Efficacy evaluation should be performed once every 2 cycles (6 weeks \pm 7 days) in the first 12 months (first 16 cycles) from the study treatment. Then it is performed once every 3 cycles (9 weeks \pm 7 days) after 12 months until PD (or discontinuation of the study treatment for subjects continuing the SHR-1210 after PD), lost to follow-up, withdrawal of informed consent or death.

Secondary efficacy endpoints include progression free survival (PFS), duration of response (DoR) and disease control rate (DCR).

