4.4.2 Missing assessments and unevaluable designation

When no imaging/measurement is done at all at a particular time point, the patient is not evaluable at that time point. If only a subset of lesion measurements is made at an evaluation, usually the case is also considered not evaluable at that time point, unless a convincing argument can be made that the contribution of the individual missing lesion(s) has/have no effect on the assigned time point response. This would be most likely to happen in the case of PD. For example, if a patient had three measured lesions with a baseline sum of 50 mm and only two lesions with a sum of 80 mm were assessed at a subsequent follow-up, the patient has achieved PD status, regardless of the contribution of the missing lesion.

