4.4.4 Special notes on response evaluation

When nodal disease is included in the sum of target lesions and the nodules decrease to a normal size of < 10 mm, they may still have a measurement reported on scans. This measurement should be recorded even though the nodules are normal in order not to overstate progression should it be based on increase in size of the nodules. As noted earlier, this means that subjects with CR may not have a total sum of zero on the CRF.

In trials where confirmation of response is required, repeated "NE" time point evaluations may complicate best response evaluation. The analysis plan for the trial must address how missing data/evaluations will be addressed in determination of response and progression. For example, in most studies it is reasonable to consider a subject with time point responses of PR-NE-PR as a confirmed response.

Subjects with an overall deterioration of health status requiring discontinuation of treatment without objective evidence of PD at that time should be reported as symptomatic deterioration. Efforts should be made to evaluate objective progression even after discontinuation of treatment. Symptomatic deterioration is not a description of an objective response: it is a reason for discontinuation of treatment. The objective response status of such subjects is to be determined by evaluation of target and non-target lesion as shown in Tables 1-3.

Conditions that are defined as early progression, early death and not evaluable are study specific and shall be clearly described in each protocol (depending on treatment duration and treatment cycle).

In some circumstances it may be difficult to distinguish residual lesions from normal tissues. When the evaluation of complete response depends upon this definition, it is recommended to perform a biopsy before evaluating the efficacy of complete remission of local lesions. FDG-PET

may be used to confirm a response to a CR in a manner similar to a biopsy in cases where a residual radiographic abnormality is thought to represent fibrosis or scarring. The use of FDG-PET in this circumstance should be prospectively described in the protocol and supported by disease specific medical literature for the indication. However, it must be acknowledged that both approaches may lead to false positive CR due to limitations of FDG-PET and biopsy resolution/sensitivity.

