### **6.4 Evaluable Set**

It is a subset of FAS and includes all enrolled subjects who have received the study drugs at least once and have at least one post-baseline tumor assessment.

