# 10 HANDLING OF MISSING VALUES

## 10.1 Handling of Missing Data of Tumor Assessment

When missing, the tumor assessment data will be treated according to RECIST (v1.1, refer to the table in appendix for details).

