#### **11.5.2 Secondary efficacy endpoint analysis**

##### **11.5.2.1 Disease control rate (DCR)**

DCR is defined as the percentage of subjects in the analysis population who have BOR evaluation of CR, PR, or SD.

When the response evaluation data of a subject after treatment are missing or unknown, the subject is not evaluable (NE) and will be included in the denominator for percentage calculation.

DCR and its two-sided 95% exact (Clopper-Pearson) confidence interval will be calculated.

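### SAP 11.5.1.2 makes a subject non-evaluable for ORR when only the first post-treatment assessment is missing, with no exception for a later confirmed response

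*SAP*

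**What the plan says.** SAP 11.5.1.2 defines ORR by a confirmed best overall response (BOR) of CR or PR, then adds: "When the first response evaluation data of a subject after treatment are missing or unknown, the subject is not evaluable (NE"; such a subject enters the denominator only.

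Other places treat a missing scan differently:

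- Protocol 7.1.1: "For subjects without documented progression or new anti-cancer treatment, BOR will be determined based on all response evaluations". SAP 11.5.1.1 has the same rule, and its confirmed-PR definition sets no condition on the first scan.
- SAP 10.1: "When missing, the tumor assessment data will be treated according to RECIST". The RECIST text in protocol Appendix 3, 4.4.2 says: "When no imaging/measurement is done at all at a particular time point, the patient is not evaluable at that time point".
- Protocol Appendix 3, 4.4.4, on a gap between two responses: "in most studies it is reasonable to consider a subject with time point responses of PR-NE-PR as a confirmed response".
- SAP 11.5.2.1, for DCR: "When the response evaluation data of a subject after treatment are missing or unknown, the subject is not evaluable (NE". This is almost the same sentence without the word *first*.
- SAP 11.5 has a third wording: "If a subject's baseline or post-baseline tumor assessment is missing, the subject's is non-evaluable (NE) in response". It does not say whether one missing assessment is enough.
- SAP 6.4 admits to the Evaluable Set treated subjects who "have at least one post-baseline tumor assessment", and ORR is repeated on that set.

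On stable disease, SAP 11.5.1.1 asks for SD at least once within 5 weeks of the start of the study, with a bracket giving 6 weeks minus 7 days. Protocol 7.1.2 and SAP Appendix 1.3 make the same interval a minimum.

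**The concern.** ORR is the primary endpoint, and each cohort is judged on a responder count: at least 4 of 19 at stage 1, then at least 21 of 43 (cohort 1) or 13 of 55 (cohort 2). A sentence that turns a confirmed responder into a non-responder acts directly on those counts. Two programmers, one following 11.5.1.2 and the other following 11.5.1.1 and protocol 7.1.1, could report different numbers of responders from the same data.

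The outputs would also disagree with each other. The affected subject could appear as PR in the BOR table and in DCR, and would enter the duration-of-response analysis, because SAP Table 2 asks only whether a CR or PR was confirmed. The same subject would not be a responder for ORR.

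**Working it through.** **1. One subject traced through the text.** No week-6 scan; PR at weeks 12 and 18; no progression or new therapy.

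| Rule | Result |
|---|---|
| SAP 11.5.1.2 (ORR) | NE, denominator only |
| SAP 11.5.1.1 and protocol 7.1.1 (BOR) | PR, confirmed 6 weeks later (at least 4 needed) |
| SAP 10.1 with Appendix 3, 4.4.2 | NE at week 6 only |
| SAP 11.5.2.1 (DCR) | PR, counted as controlled |
| SAP 6.4 (Evaluable Set) | included |

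**2. The plan's own design.** Inputs from protocol 8.2 and SAP 5: P0 = 35% and P1 = 55% (cohort 1), P0 = 15% and P1 = 30% (cohort 2), with the counts above. The probability of a positive verdict at response rate p is

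sum over x = 4 to 19 of Bin(x; 19, p) × P(Y ≥ R − x), with Y ~ Bin(N − 19, p).

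- Cohort 1 (N = 43, R = 21): power 0.8329, one-sided type I error 0.0429.
- Cohort 2 (N = 55, R = 13): power 0.8006, type I error 0.0477.

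Both meet the stated 80% and 0.05.

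**3. With the sentence applied literally.** Let f be the share of confirmed responders removed. The documents give no value, so f is an assumption. The rate becomes p(1 − f); for example, cohort 1 at f = 5% has 0.55 × 0.95 = 0.5225.

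| f | Cohort 1 power | Cohort 1 type I | Cohort 2 power | Cohort 2 type I |
|---|---|---|---|---|
| 0 | 83.3% | 4.3% | 80.1% | 4.8% |
| 2% | 79.4% | 3.5% | 77.8% | 4.2% |
| 5% | 72.6% | 2.5% | 74.0% | 3.4% |

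Power and type I error both fall. These figures hold for exactly 43 and 55 subjects analysed.

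**4. One reclassified responder.** If exactly one randomly chosen responder is removed, a positive verdict at P1 is lost with probability 8.7% (cohort 1) or 7.9% (cohort 2). For cohort 2, 5.4 points come from a total of exactly 13; the rest comes from falling to 3 of 19 at stage 1. These probabilities are conditional on a reclassification and on the same sample sizes.

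**5. Dependence on the number analysed.** Protocol 8.2 enrols 48 and 62 to allow for 10% non-evaluable subjects. If all of them were counted against the unchanged cut-offs of 21 and 13, power at f = 5% would be 90.7% and 80.3%. The table in step 3 does not apply to that case.

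**6. Stable disease.** The first scan is due at 6 weeks ± 7 days, that is, days 35 to 49. An upper limit of 5 weeks is day 35, so only 1 of these 15 days satisfies both the literal upper limit and the minimum. Read literally, SD at week 6 followed by PD at week 12 misses the SD rule and falls into the PD category of 11.5.1.1.

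**The case against.** The strongest reply is that 11.5.1.2 should be read with its surroundings. It opens by defining ORR through confirmed BOR, 11.5.1.1 takes BOR from all evaluations and leaves NE for whatever remains, and the rest of the plan agrees. On that view the sentence means only that no post-treatment evaluation was obtained. This is probably the intent, but the sentence names the first evaluation and provides no exception.

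The rule also has limited reach. SAP 9.5 summarises visits as recorded even when outside the window, and replaces a missing planned visit with the nearest unplanned one. The rule therefore applies only when neither a late scan recorded under the first visit nor an unplanned scan fills it, and it changes ORR only if that subject later has a confirmed response. This stands as a limit on size; it does not remove the contradiction.

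The 10% allowance might absorb the loss. If NE subjects were replaced until 43 and 55 evaluable subjects remained, and missingness were unrelated to response, most of it would disappear. But 11.5.1.2 keeps these subjects in the denominator, so replacement cannot be assumed.

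Some stronger readings are tempting and not supported:

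- A reader might infer that the trial is underpowered. The documents give no rate of missed first scans, and the power figures hold only at 43 and 55.
- A reader might infer that the rule favours the treatment. It only removes responders.
- A reader might see a gap in SAP Appendix 1.3, where the only row beginning with NE is NE then NE. The columns are previous and subsequent time points, so NE-PR-PR is covered by the PR-then-PR row.

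**Conclusion.** Wrong as written, and it should be corrected before database lock. The contradiction follows from the text alone. Compared with using all evaluations, the rule cannot turn a negative result positive; its cost is power and an ambiguous responder count.

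The size rests on an assumed f and on exactly 43 and 55 analysed. At f = 2% to 5%, cohort 1 loses about 4 to 11 points of power (83.3% to 79.4% or 72.6%) and cohort 2 about 2 to 6 points (80.1% to 77.8% or 74.0%). If no responder lacks a first evaluation, nothing changes.

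The SD wording is secondary. The bracket in 11.5.1.1 suggests that a minimum was meant. It affects DCR and the BOR table, neither of which has a decision rule.

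**What to change.** **Main point.** Delete *first* in SAP 11.5.1.2 and use one text in 11.5, 11.5.1.2 and 11.5.2.1, for example: *A missing or NE scan is NE at that time point only. BOR uses all evaluable assessments up to and including first PD and before any new anti-cancer therapy. BOR is NE if the baseline assessment is missing, if there is no evaluable post-baseline assessment, or if no other BOR category is met under Appendix 1.3.*

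**SD.** Reword the bullet in 11.5.1.1 as *SD at least once at or after 5 weeks (6 weeks minus 7 days)*, counted from one start date used in both documents. At present protocol 7.1.2 counts from enrollment, SAP 11.5.1.1 from the start of the study and SAP Appendix 1.3 from the start of treatment.

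**SAP Appendix 1.3.** Add a row for SD then PD: SD if the minimum time is met, otherwise PD. In the row for PR then missing, which now gives SD without a time condition, write SD if the minimum time is met, otherwise NE. That agrees with protocol Appendix 3, Table 3.

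**Cost.** A few SAP sentences and two table rows, with no new data. Deleting *first* brings the SAP into line with protocol 7.1.1 and needs no protocol change. Protocol 7.1.2 needs a matching edit only if the chosen SD start date is not enrollment.

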#### **11.5.2 Secondary efficacy endpoint analysis**

##### **11.5.2.1 Disease control rate (DCR)**

DCR is defined as the percentage of subjects in the analysis population who have BOR evaluation of CR, PR, or SD.

When the response evaluation data of a subject after treatment are missing or unknown, the subject is not evaluable (NE) and will be included in the denominator for percentage calculation.

DCR and its two-sided 95% exact (Clopper-Pearson) confidence interval will be calculated.

##### **11.5.2.2 Duration of response (DoR)**

DoR is defined as the time from first documented evidence of CR or PR until the date of first documented evidence of progressive disease or death due to any cause. The end date of response must be consistent with the date of progressive disease or death of PFS. Tumor response is based on the confirmation, and the response that has not been confirmed will not be included. The date of response is the date of first observation (the last date of imaging assessment of visit, not the date of visit), not the date of confirmation. [Table 2](#) describes information on progressive disease, death, or censoring.

For DoR, survival curves will be plotted using the Kaplan-Meier method and the 95% CI for median time will be calculated using the Brookmeyer-Crowley method. In addition, a swimmer plot will be drawn for each cohort.

Way to interpret [Table 2](#): From the first question until the occurrence of progressive disease, death or censoring, and the corresponding date.

**Table 2. Progressive disease and censoring of the duration of response**

		No	Yes
1.	Has the subject's response evaluation been confirmed as CR PR?	Not included in the analysis	Skip to 2
2.	Are new anti-cancer drugs used before progressive disease or death?	Skip to 3	Censoring The date of censoring is the date of the last objective tumor assessment before the use of the new anti-cancer drug
3.	Has the subject experienced progressive disease?	Skip to 5	Skip to 4
4.	Is the progressive disease of the subject recorded after an unacceptably long time interval (the response evaluation is missing by > 2 times, i.e., 98 days)?	The end date of response is the date of progressive disease	Censoring The date of censoring is the date of the last objective tumor assessment before the long-term lost to follow-up
5.	Is the subject dead?	Censoring The date of censoring is the date of the last objective tumor assessment	Skip to 6
6.	Is the death of the subject recorded after an unacceptably long time interval (the response evaluation is missing by > 2 times, i.e., 98 days)?	The end date of response is the date of death	Censoring The date of censoring is the date of the last objective tumor assessment before the long-term lost to follow-up

### 11.5.2.3 Progression free survival (PFS)

PFS refers to the time from the start of randomization to the date of objective progressive disease or death (caused by any reason), whichever occurs first. [Table 3](#) describes progressive disease, death, or censoring.

**Table 3. Date of progressive disease, death, or censoring**

		No	Yes
1.	Does the subject have a baseline objective tumor assessment?	Censoring The date of censoring is the date of randomization	Skip to 2
2.	Are new anti-cancer drugs used before progressive disease or death?	Skip to 3	Censoring The date of censoring is the date of the last objective tumor assessment before the use of the new anti-cancer drug
3.	Has the subject experienced progressive disease?	Skip to 5	Skip to 4
4.	Is the progressive disease of the subject recorded after an unacceptably long time interval (the response evaluation is missing by > 2 times, i.e., 98 days)?	Progressive disease The date of progression is the date of earliest recorded progressive disease	Censoring The date of censoring is the date of the last objective tumor assessment before the long-term lost to follow-up
5.	Is the subject dead?	Censoring The date of censoring is the date of the last objective tumor assessment	Skip to 6
6.	Is the death of the subject recorded after an unacceptably long time interval (the response evaluation is missing by > 2 times, i.e., 98 days)?	Progressive disease The date of progression is the date of death	Censoring The date of censoring is the date of the last objective tumor assessment before the long-term lost to follow-up

The time of PFS is based on the time of the imaging examination rather than the time of the visit. The RECIST imaging examination time (targeted lesion, non-targeted lesion, and new lesion) for a special visit may be different, and the following rules apply:

- The date of progression will be based on the earliest date leading to progression.
- The date of censoring will be based on the last date of objective tumor assessment.

Survival curves will be plotted using the Kaplan-Meier method and the 95% CI for median time will be calculated using the Brookmeyer-Crowley method.

